Ethnographic methods (field observation, opportunistic and semi-structured interviews) will be used. Such methods are uniquely suited to the study of organizational behavior as they facilitate in-depth understanding of change processes, workflows and routines, and barriers and facilitators to change. At these visits, we will explore the implementation process, toolkit use and barriers and enablers of practice change, including understanding clinic workflow for DM / CVD patients, and how ALL supports medication decision-making.

Additional interviews. In years 3-4.5, our qualitative team will conduct telephone or video-based semi-structured interviews with staff at each CHC that we do not visit in person. The interviews will be designed to elicit further information about how ALL was implemented, how effectively each arm's strategy supported that implementation, and barriers to effectiveness. We will also likely conduct more informal, follow-up interviews to fill in knowledge gaps identified during subsequent data collection and analysis.

Other qualitative data sources. Our team will also collect 'archival' data related to the process evaluation (e.g., email / telephone discussions with CHC staff; clinic policies; concurrent QI initiatives, as well as conduct regular debriefings with practice facilitators (arm 3)).

Quantitative data: This data will be extracted monthly from OCHIN's EHR will include: (a) Study population identification (age, CVD / DM, prescriptions); (b) Patient and (c) Clinic characteristics; (d) Patient outcomes

(last BP, LDL results and measurement dates; issued prescriptions and dates); and (e) Process measures (e.g., tool use, encounters). Cost data will be collected as well.

7. Data Analysis

a. Analysis Plan

Describe the data analysis plan, including any statistical procedures.

When applicable, provide a power analysis.

Describe any procedures that will be used for quality control of collected data.

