Statistical power. Segmented regression is a powerful statistical technique in diverse applications, but formal power analyses may not be feasible as estimates of the model parameters are not available prior to the study. We will meet or exceed the 12 points pre- and post-intervention used in similar segmented regression analyses, as is adequate to detect even modest effect. To illustrate our power to detect changes between study arms, we conducted a

power analysis using data from our current study. At 12 months post-intervention, 60%, 63% and 46% of control clinic patients and 68%, 76%, and 58% of intervention clinic patients were appropriately on statins, ACE, and both, respectively. We can detect differences of this magnitude between any two arms of the study with power of .95 to .99 if the intra-class correlation is .01, and power of .76 to .99 if the ICC is .02 with an alpha level of .05.

Additional analyses (Minimal support needed to achieve treatment thresholds): While our primary analyses will measure implementation impact as described above, we will also conduct secondary analyses, for both the patient health and guideline-based prescribing outcomes, in which we will define thresholds of intervention impact. Thresholds will be defined as a target percentage of clinic patients with (i) guideline-appropriate prescriptions; (ii) last LDL <100; and (iii) last systolic BP <135. Targets will be determined based on baseline data and in consultation with the SPREAD-NET advisory group, which includes CHC clinicians. We will then assess the minimal amount of implementation support needed to achieve threshold results. We anticipate based on our first study that these targets will be approximately (i) 75%; (ii) 70%; and (iii) 80%, respectively. Logistic regression will be used, with study arm (reference group = High support) predicting a binary outcome for threshold achieved by 12 months.

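### The secondary minimal-support analysis reduces each clinic's 12-month percentage to yes/no with about 10 clinics per arm, which costs precision about reaching the target that a continuous clinic-level model would keep

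*Combined protocol and SAP*

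**What the plan says.** Section 7a, Additional analyses, introduces the work as secondary: "we will also conduct secondary analyses, for both the patient health and guideline-based prescribing outcomes, in which we will define thresholds of intervention impact". The threshold belongs to the clinic: "Thresholds will be defined as a target percentage of clinic patients with (i) guideline-appropriate prescriptions; (ii) last LDL <100; and (iii) last systolic BP <135". The purpose follows: "We will then assess the minimal amount of implementation support needed to achieve threshold results". The method is one sentence: "Logistic regression will be used, with study arm (reference group = High support) predicting a binary outcome for threshold achieved by 12 months".

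The targets are not yet fixed. "Targets will be determined based on baseline data and in consultation with the SPREAD-NET advisory group", and "We anticipate based on our first study that these targets will be approximately (i) 75%; (ii) 70%; and (iii) 80%, respectively".

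The plan gives no power for this analysis and names no small-sample method. It does not say whether the deadline means the month-12 percentage or any month up to month 12. Of the outcome data, section 6 says "This data will be extracted monthly from OCHIN's EHR". The Aim 1 model in section 7a (Specific Aim 1 & 2 analyses) is a three-level segmented regression on uncut data. It compares changes in level and slope between arms and makes no reference to a target.

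**The concern.** A percentage of a clinic's patients is a clinic-level quantity, so each clinic contributes one yes/no value, about 10 per arm. The percentage behind it is well measured, since it rests on several hundred patients. After the cut, a clinic 1 point short of target scores the same as one 25 points short, and the opposite of one 1 point above.

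This is the only named analysis tied to a target, so the statement about minimal support rests on it. Two things are at stake. The estimated share of clinics reaching target in each arm is noisier than the data require. And because High support is the reference, a reader might take a non-significant difference for Low or Medium as evidence that less support is enough, when the analysis had little chance of showing otherwise.

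**Working it through.** **Inputs from the documents.** 30 clinics in 3 arms (section 5a); about 20,000 patients (section 5b). From Statistical power in section 7a: ICC .01 or .02; alpha .05; planning rates for statins 60% v 68%, ACE 63% v 76%, both 46% v 58%.

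**Assumptions.** Equal allocation, so 30/3 = 10 clinics per arm; 20,000/30 = about 667 patients per clinic; two-sided testing; the month-12 percentage; one pair of arms at a time.

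**The plan's own power figure.** Effective n per arm = 10 × 667 / (1 + 666 × ICC).
- ICC .01: 6,670/7.66 = 871. Statin power is .936 (the plan's lower end is .95).
- ICC .02: 6,670/14.32 = 466. Statin power is .721 (the plan's lower end is .76, so 4 points short).
- The other effects give .999 to 1.00 at ICC .01 and .957 to .991 at ICC .02, in line with the plan's upper ends.

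The .76 is therefore not reproduced. This does not drive the point, because the loss below compares two analyses on identical inputs.

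**Power after the cut, statins, target 64%.** The midpoint is used because it is close to the kindest case for a yes/no cut; it is not a proposed target. A clinic percentage is taken as normal with mean p and variance p(1 − p)[ICC + (1 − ICC)/667]; q = P(percentage ≥ target).
- ICC .01: SDs are √(.24 × .01148) = .0525 and √(.2176 × .01148) = .0500, so q = .223 and .788.
- ICC .02: SDs are √(.24 × .02147) = .0718 and √(.2176 × .02147) = .0683, so q = .289 and .721.

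Yes/no power is exact enumeration over Binomial(10, q) in each arm. The uncut comparison is a simulated two-sample t-test on the same clinics.

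| Analysis | ICC .01 | ICC .02 | Type I error (rates .60 to .68) |
|---|---|---|---|
| t-test on percentages | .91 | .67 to .68 | .05 |
| Logistic, likelihood ratio | .76 | .51 | .05 to .09 |
| Logistic, score | .745 | .48 | .03 to .04 |
| Logistic, Wald | .58 | .41 | .005 to .04 |
| Fisher (not named in the plan) | .56 | .295 | about .01 |

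The likelihood-ratio test loses 15 and 17 points, the score test about 17 and 19 to 20, and the Wald test about 33 and 26 to 27. A beta-binomial model of clinic rates gives the same to within a point. Over targets of 62% to 66% the loss is 14 to 17 points (likelihood ratio) and 17 to 23 (score). With 10 v 9 clinics, since section 5d counts 29, it is 11 to 12 points for both tests at 64%.

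**Other planning effects, likelihood-ratio and score tests.**
- ACE, target 70%: .99 v 1.00 at ICC .01 (about 1 point); .90 to .91 v .98 at ICC .02 (7 to 8 points).
- Both drugs, target 52%: .96 to .97 v 1.00 (about 3 points); .79 to .81 v .94 (13 to 15 points).

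**Precision of the probability that a clinic reaches target.** The raw share has variance q(1 − q)/10. The alternative is Φ((arm mean − target)/SD), with SD pooled over three arms (third arm placed midway). For statins at 64%:

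| Arm, ICC | Raw share, root MSE | Model-based, root MSE | MSE ratio |
|---|---|---|---|
| 60%, .01 | .132 | .099 | 1.77 |
| 68%, .01 | .129 | .096 | 1.82 |
| 60%, .02 | .143 | .111 | 1.67 |
| 68%, .02 | .142 | .107 | 1.77 |

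A ratio of 1.7 to 1.8 is what the raw count would gain from 17 to 18 clinics per arm instead of 10. Bias of the model-based estimate was about 1 point here, and about 2 points at most across the scenarios tried.

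**The case against.** The best reply is that the t-test answers a different question. When arms are compared on distance from target, the target cancels, and Aim 1 already compares arms on the uncut scale with 24 pre-implementation months and covariates. This stands. A reader might infer that the trial cannot separate its arms; the documents do not support that, and the cost is better stated as precision about reaching the target.

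Second, a reader might put the loss at up to 40 points. That figure comes from Fisher's test, which the plan does not name and whose type I error here is about .01, so much of it is conservatism rather than the cut. The Wald loss is partly a small-sample artefact too, since the test breaks down when an arm has nearly all or no clinics at target.

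Third, at the anticipated 75% target statin power is at most .04 (ICC .01) or .16 (ICC .02) under any of these tests. A reader might blame the cut, but this is mainly where the target sits, and the plan calls 75% approximate and leaves it to be set.

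Fourth, whether a clinic reached an agreed target is a legitimate, readable endpoint, and a raw count needs no normality assumption. This also stands, and is why the count should stay.

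**Conclusion.** The point holds, as a worthwhile and inexpensive improvement to a secondary analysis. It is not a flaw in the primary model. For the statin effect with a midpoint target, the cut costs about 15 to 20 points of power under a likelihood-ratio or score test. The loss is about 1 to 8 points for ACE at 70% and 3 to 15 for both drugs at 52%. The main cost is a mean squared error about 1.7 to 1.8 times larger than necessary for the probability that a clinic reaches target. That is roughly 40% to 45% of the information (1 − 1/1.7 = .41; 1 − 1/1.8 = .44), so it would be too strong to say that most of it is lost.

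The sizes rest on equal allocation, about 667 patients per clinic, two-sided .05, roughly normal clinic percentages, and the month-12 reading of the deadline. With 29 clinics the low end of the statin loss falls to about 11 points.

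**What to change.** Keep the targets, and keep reporting the number of clinics at target in each arm. Add, for each outcome, a clinic-level linear model of the month-12 percentage with arm as a factor. For each arm report:
- the mean distance from target with a 95% CI;
- the model-based probability that a clinic reaches target, Φ((mean − target)/SD) with the pooled between-clinic SD, with a bootstrap or delta-method CI.

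Base the minimal-support statement on these two results. State that they refer to the month-12 percentage, because reaching the target in any month up to 12 is a different quantity that this formula does not estimate.

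The cost is a few sentences of plan wording and a little analysis time. No new data are needed, since the percentages must be computed before they can be cut. The downside is that the modelled probability assumes roughly normal clinic percentages, which matters most for targets in the tail; a logit transform or bootstrap serves as a check.
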